In addition, attractive and informative packaging plays a crucial role in building a brand name (Keller KL, 2005). Studies have shown that recognized and reputable brand names are associated with increased consumer acceptance and adherence compared to generic drugs (Rafael GB et al, 2019; Faasse K, et al, 2013; Faasse K, et al, 2016). Thus, understanding women's and their partners' preferences regarding packaging design can help create a brand for antenatal MMS that is delivered through the national health system that promotes optimal use throughout pregnancy.

2. Study aims and objectives

This study aims to assess the relevance, acceptability, and utility of three interventions in supporting adherence to the MMS regimen of one tablet per day. The overall aims of the study are to:

1. Learn what pregnant women prefer regarding visual reminders and motivational messages to help them remember to take their MMS.
2. Identify challenges and supports that affect whether women can take their MMS daily throughout their pregnancy.
3. Work with end users (pregnant women) to design motivational messages and visual reminders that are culturally appropriate and relevant for the local community. These will be designed to help women consistently take one MMS tablet each day for the entire 180 days of their pregnancy.
4. To collect feedback from pregnant women and their partners regarding the packaging design for antenatal MMS delivered through the national health system. This feedback will be used to help finalize the MMS packaging design, including the color scheme, logo, brand name, and packaging features.

3. Study design

This is a longitudinal mixed-method study that uses a cross-over TIPS design. All enrolled pregnant women will be asked to take MMS for the duration of their pregnancy and will experience all three interventions in a specific order. In this way, everyone gets to experience each approach. The women will receive exposure to each intervention for 3-4 weeks. On approximately the fourth week, eighth week, and twelfth week of the study, the pregnant women will be asked to participate in a focus group discussion (FGD) with other women in the province who also received the same intervention the previous weeks. This process will be iterated in the same way for Intervention A, Intervention B, and Intervention C.

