- Approximately 3 social media videos and posts will be developed.
- The videos and posts might cover topics like:
 - The importance of MMS for maternal health and growing baby's health.
 - Benefits of consistent medication adherence.
 - Benefits of healthy eating.
 - General pregnancy care information and warning signs.
 - Reminders to attend prenatal checkups.

After using each intervention for 3-4 weeks, women will be invited to a FGD to share their experiences. The discussion will focus on whether they liked the intervention, how well it helped them remember to take their MMS and any pros and cons they saw. It will also ask the women to compare the current intervention with other intervention (i.e. family support, wall calendars, and public service announcements). Adherence data will be collected by asking women to bring their MMS pill bottle to the FGD for counting. Acceptability data will be collected through a Likert survey and will be administered by a member of the study team.

By using this TIPS crossover design, researchers can see which approach works best and use the women's feedback to improve the program throughout the study. This collaborative process, where participants try different interventions and share their experiences, allows researchers to refine the program iteratively (meaning in steps) based on the feedback, resulting in a more effective program by the end of the study.

4. Study setting

The research will be conducted in Kampong Chhnang, Rattanakiri, Takeo, and Kampot, representing the four regions in Cambodia: Coastal, Upland (Northeast), Lowland, and Tonle Sap.

5. Sample size calculation and sampling process

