9-11	C	Same women	Same women	Same women	Same women	
12	Focus Group Discussions					
Total		12-15	12-15	12-15	12-15	48-60

The study participants will include approximately 48-60 pregnant women attending their first ANC in their first trimester at a public health center. Approximately 48-60 pregnant women will be recruited across 4 health centers in Kampong Chhnang, Rattanakiri, Takeo, and Kampot. It is estimated that approximately 12-15 pregnant women will be enrolled per province. Pregnant women will be purposively recruited at their **first antenatal care visit** (~8-14 weeks gestation). An attempt will be made to select women of diverse sociodemographic characteristics.

For the participatory workshops to co-design the MMS package, we plan to invite all women and their husbands enrolled in the TIPS study design. The first 25 from each province who agree to participate will be registered to attend the participatory workshop. We will aim to have a relatively equal proportion of men and women.

6a. Inclusion criteria for pregnant women

- Age 18-45 years
- Attending first ANC
- Low-risk pregnancy, which includes being pregnant with a single pregnancy and the absence of any other medical or surgical conditions
- Reside in Kampong Chhnang, Rattanakiri, Takeo, and Kampot and not planning to move away within four months
- Agree to try to take MMS as their prenatal supplement
- Agree to participate in three FGDs, one every three months
- Agree to bring MMS bottles to the FGD each month for tablet counting

6b. Exclusion criteria for pregnant women

- Pregnant women who do not fall into the age range of 18-45
- Came to the health facility after first ANC
- Midwives and/or doctors have classified pregnant women as having a high-risk pregnancy.

6c. Inclusion criteria for husbands

- Willingness to participate in the participatory workshop
- Confirmed availability for date and time of workshop

6d. Exclusion criteria for husbands

- Unwillingness to participate in the participatory workshop
- Did not confirm availability for the date and time of workshop

6e. Recruitment process and taking informed consent

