There is no allocation to any intervention group. Each enrolled woman receives all interventions in a specific sequence. Per province, in each health facility, the study team will purposively select pregnant women to ensure a diversity in sociodemographic characteristics. This helps ensure the interventions are appropriate for a broad range of women. After ensuring written informed consent, the eligible pregnant women will be asked to participate in taking MMS and arm experience all three interventions (A, B, and C) in a specific order. The sequence for each study arm and their exposure to the intervention is shown in Figure 2. This allows researchers to compare a participant's experience with each intervention.

7b. Enrollment data

Demographic and other enrollment data, such as gestational age at enrollment, maternal age, maternal BMI, maternal Hb, parity, as well as contact information and detailed directions to home of residence, will be collected from the health facility. This data will be included in the analysis for adherence, acceptability, and barriers and enablers.

7c. Intervention description

- **Intervention A (MMS + Family support):** 180 tablets of MMS and daily encouragement and help from family members. Family members will receive an orientation on supporting pregnant women and encouraged them to provide daily motivational reminders until she finished 180 pills
- **Intervention B (MMS + Visual reminders):** 180 tablets of MMS and wall calendars with health information and motivational messages will be provided.
- **Intervention C (MMS + Social media posts and videos):** 180 tablets of MMS and 2-3 times/weekly social media posts and videos educational and motivational messages from healthcare providers delivered through social media posts and videos. Messages will emphasize its benefits and offer encouragement.

Figure 2: Weeks 1-14, Testing of interventions across all study arms and participant FGDs

Intervention	Week 1-3	Week 4	Week 5-7	Week 8	Week 9-11	Week 12	Week 13-14
A	Intervention A	Focus Group Discussion A	Intervention B	Focus Group Discussion B	Intervention C	Focus Group Discussion C	Participatory Workshop
B	X	X					X
C			X	X	X	X	X

7d. Conduct of focus group discussions

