From pill count data, descriptive analysis will be performed to measure daily adherence to MMS. During each focus group discussion, we will count the MMS tablets for each participant and calculate the eligible period for consumption from the 1st ANC date (pill received date) to the date of the focus group discussion. The mean number of tablets consumed will be calculated based on the eligibility of the consumption period. Adherence will be measured after the completion of each intervention, and differences in the mean will be measured. However, due to a very low sample size, no statistical test will be applied.

10c. Acceptability data

At the first focus group discussion, data collectors will ask pregnant women a quantitative acceptability questionnaire about MMS. A descriptive analysis will be conducted to determine the level of agreement (%) with each statement. However, due to a very low sample size, no statistical test will be applied.

11. Data custody, security, and protection of subject confidentiality

All data gathered during the study will be connected to identifiers and treated with the utmost confidentiality throughout and beyond the study period. Only the study's PIs and Co-PIs will have access to the data linked to the identifiers. The results of any analyses, presentations, or papers will be presented in aggregate to prevent individual disclosure. The survey will collect names of pregnant women only to ensure the accountability of the study team and to avoid duplication in the data collection/interviewing process. This information will be replaced with anonymous ID numbers for analysis, and the original data will be disposed of. Only members of the study team will be given access to the data.

Any paper notes collected during interviews will be kept in a locker until the final analysis is done. Once the analysis is done, all paper forms will be cut into pieces using a paper shredder machine. The data entry web-based platform will be password protected, and only a designated person can enter data. The data focal person will only have access to download and clean.

12. Risks and Benefits

Overall, the potential benefits of this study outweigh the minimal risks.

Benefits:

- Improved micronutrient status and improved birth outcomes: MMS is a proven effective intervention that improves maternal micronutrient status as well as improves birth outcomes, specifically reduces low birth weight, small for gestational weight, and pre-term births.

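### With one fixed order A, B, C, lasting family support and tablet counts that start at first ANC, the planned differences in mean adherence cannot be attributed to any single intervention

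*Combined protocol and SAP*

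**What the plan says.** - **Order.** Section 7a: "There is no allocation to any intervention group. Each enrolled woman receives all interventions in a specific sequence". Figure 1 in Section 6 shows A in weeks 1-3, B in weeks 5-7 and C in weeks 9-11 for the same women in all four provinces. No washout or MMS-only period is described.
- **Duration.** Section 3: "The women will receive exposure to each intervention for 3-4 weeks". Section 7c, however, has family members "provide daily motivational reminders until she finished 180 pills".
- **Adherence measure.** Section 10b will "calculate the eligible period for consumption from the 1st ANC date (pill received date) to the date of the focus group discussion", and then: "Adherence will be measured after the completion of each intervention, and differences in the mean will be measured". It plans no test; the only reason and the only caveat given is the small sample.
- **Purpose.** Section 2 opens with the "utility of three interventions in supporting adherence to the MMS regimen of one tablet per day". Section 3 says: "By using this TIPS crossover design, researchers can see which approach works best".
- **Start of tablets.** Under Section 6e tablets are handed out at first ANC, and written consent may follow up to two weeks later. Section 7a places the interventions after written consent.

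**The concern.** A crossover separates treatment from period by giving different participants different orders. Here there is one order, so the label B and the label second period describe the same observations. A change in adherence between counts could reflect the intervention, the stage of pregnancy, growing habit or fatigue with the tablets, or support left over from the previous period. Leaving out a test because the sample is small does not deal with this: more women would give the same bias with more precision.

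Two further features compound the problem. If family reminders really continue to the last tablet, the B and C periods are A plus B and A plus C. And if each adherence figure is computed from first ANC, the figure reported after B or C is an average over everything that came before.

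At stake is the plan's only numerical measure of adherence, in a document that says the design shows which approach works best. Real gains could be shrunk, and interventions that help equally could appear to differ.

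**Working it through.** **Inputs from the documents.** FGDs in weeks 4, 8 and 12; enrolment at about "8-14 weeks gestation" (Section 6); 180 tablets; 48-60 women; 20% expected not to attend (Section 5). The stated sample size reproduces: 4 × 12 = 48 and 4 × 15 = 60. There is no adherence figure in the plan to reproduce.

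**Assumptions for illustration.** Three periods of 28 days. The lead L from tablet issue to the start of A is 0 or 14 days, the upper value taken from the two-week consent allowance. An intervention effect is 10 percentage points, effects add without a ceiling, there is no drift unless stated, and there is no gain during the lead. Results scale with the 10 points.

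**Step 1: order.** With four province terms, two period terms and two intervention terms, the design with A, B, C everywhere has rank 6 for 8 parameters. Neither B-A nor C-A can be estimated. Each woman is eight weeks further into pregnancy in period C than in period A: 8-18 weeks' gestation for A and 16-26 for C with no lead, with upper ends of 20 and 28 if A starts 14 days late.

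**Step 2: cumulative reading.** If the gains in the three periods are g1, g2 and g3, the reading after period k is 28 × (g1 + … + gk) / (L + 28k).

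| Scenario | True gains by period | Reading, L = 0 | Reading, L = 14 |
|---|---|---|---|
| Gain in C only | 0, 0, 10 | 0, 0, 3.3 | 0, 0, 2.9 |
| Gain in B only | 0, 10, 0 | 0, 5.0, 3.3 | 0, 4.0, 2.9 |
| Equal effects, A persists | 10, 20, 20 | 10, 15, 16.7 | 6.7, 12.0, 14.3 |
| Equal effects, no carry-over | 10, 10, 10 | 10, 10, 10 | 6.7, 8.0, 8.6 |

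In the third row the interventions are equally effective, yet B-A is 15 − 10 = +5.0 and C-A is 16.7 − 10 = +6.7. With the lead they are 12.0 − 6.7 = +5.3 and 14.3 − 6.7 = +7.6.

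**Step 3: the other reading of 10b.** Suppose the differences are taken between successive mean tablet numbers. With assumed true adherence of 70, 80 and 90% and no lead, cumulative tablets are 19.6, 42.0 and 67.2. Successive differences are 22.4 and 25.2 tablets, which are 80% and 90% of 28, so nothing is diluted. Cumulative rates would read 70, 75 and 80%.

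**Step 4: drift defeats both readings.** Let no intervention have any effect while adherence falls 85, 80, 75%. Cumulative rates read 85, 82.5 and 80%; interval rates read 85, 80 and 75%. Either way A looks best. For a linear drift of d per period, the false C-A is d on cumulative rates and 2d on interval rates. The documents give no value for d.

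**Step 5: interval adherence.** This is the fall in tablet count divided by the days between counts. In the last row of the table with L = 14, the first interval runs from tablet issue and gives 280/42 = 6.7; the others give 10 and 10. That is a false 3.3 points against A. With A persisting and no lead, the intervals read 10, 20 and 20, so the false differences are +10 and +10.

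**The case against.** The strongest reply is that this is formative, mainly qualitative work. Section 10b is descriptive, Section 7a speaks of comparing women's experience, and the Section 3 statement about what works best goes on to mention their feedback. That stands in large part. A reader might infer that the study fails its aims or would choose the wrong programme. The documents do not support that: none of the four numbered aims depends on the adherence differences, and no passage uses them to select an intervention.

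A second reply is that dilution is not certain. This also stands. A reader might take it as settled that the B and C figures are diluted, but 10b can be read as differencing successive mean tablet numbers (Step 3), and the text does not say which is meant. The order and carry-over problem holds on either reading.

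Third, cumulative adherence is a legitimate quantity. Section 8 says the pill count assesses the daily regimen, and aim 3 in Section 2 concerns all 180 days. Interval figures should therefore be added, not substituted; they also show drift and persistence more strongly.

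Finally, Section 7a mentions study arms and Figure 2 has a row for each letter, which might suggest several sequences. The statement that there is no allocation, together with Figure 1, outweighs that, though the wording needs reconciling.

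**Conclusion.** The planned differences in mean adherence cannot be attributed to A, B or C. That follows from the fixed order alone and is made worse by the continuing reminders in Section 7c; it rests on no numerical assumption. The mixing of earlier periods into the B and C readings is conditional on the more natural reading of 10b. Its size is illustrative: a 10-point gain confined to C reads as 2.9-3.3 points, and three equal effects with A persisting give false differences of 5.0-5.3 (B-A) and 6.7-7.6 (C-A), for leads of 14 and 0 days and 28-day periods. The consequence is a misleading reported figure. It should be fixed, but it does not undermine the FGD findings, which stand subject to the fixed order in which women met the interventions.

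**What to change.** 1. **Section 3.** Limit the statement about what works best to women's stated preference and feedback, and do not present adherence as a crossover comparison.
2. **Section 10b.** Keep the cumulative figure, described as adherence to the whole regimen to date. Add interval adherence as defined in Step 5. Start the first interval at the pill-received date, record the date A began, and say that this interval includes any MMS-only days before A. Report by study period with the number of women per interval, and name fixed order and carry-over as limitations.
3. **Tablet issue.** Confirm whether the 180 tablets listed under each intervention in Sections 3 and 7c are the single issue described in Section 6e. Subtraction depends on it: at one tablet daily with no lead, the count should go from 152 to 124 across period B, but a second issue of 180 would make it 152 + 180 − 28 = 304.
4. **Reconcile** Section 7c with Section 3 on how long A lasts; state whether the calendar stays in use after its period; and bring the references to study arms and Figure 2 into line with Section 7a and Figure 1.

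**Cost.** Wording, one extra recorded date, and arithmetic on counts already planned; no added women, visits or FGDs. The B and C intervals each need a count at both ends. At 20% non-attendance, 0.8 × 0.8 = 64% of women have both if absences are independent, and 80% if the same women are absent: from 0.64 × 48 ≈ 31 to 0.80 × 60 = 48 women. Interval figures also show any trend or carry-over in full, so they should not be published without the period labels and the limitation.

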For the TIPS, the sample size of 48-60 women (around 12-15 women per province) is purposive but has been selected for two reasons. First, the sample size of 12-15 women per province allows enough women to participate in a FGD. Considering that an ideal number for FGD is 8-10 people if 20% of the participants are expected not to show, there would still be enough participants to conduct an FGD. Second, based on previous formative research with pregnant women in Kampong Thom, there was not much variation in the experiences of women regarding MMS acceptability and their perceptions of the benefits of various strategies to improve adherence. Thus, one FGD per province is believed to be sufficient to capture the range of perspectives on the different interventions and achieve saturation, or the point at which no new significant themes or insights emerge from the data.

For the participatory workshops to design the MMS product package, approximately 100 participants will be recruited across four provinces in Cambodia (25 participants per workshop, 4 workshops total). Participants will be pregnant women who have previously participated in the TIPS program and their husbands/partners. The sample size is a convenience sample and chosen for the following reasons. First, it is anticipated that with a focused group like pregnant women and their partners who have a shared experience with the TIPS program, 25 per province is likely enough to reach saturation. Second, the study must consider logistical manageability and group dynamics. With 25 participants, workshops can maintain a manageable size for group discussions and activities. This allows for active participation, ensures everyone has a chance to be heard, and facilitates effective interaction. Thirdly, smaller workshops require fewer facilitators, materials, and space, making them more cost-effective and easier to organize across four different provinces.

6. Participant recruitment and selection

The research team will aim to recruit 12-15 pregnant women attending their first ANC per province. Ideally, from 8-10 of these women will then join the FGD to discuss their experiences with that specific intervention (see Table 1).

Figure 1. TIPS sample size per province

Week	Interventions	Kampong Chhnang	Rattanakiri	Takeo	Kampot	Total
1-3	A	12-15	12-15	12-15	12-15	48-60
4	Focus Group Discussions					
5-7	B	Same women	Same women	Same women	Same women	
8	Focus Group Discussions					

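### Section 10b compares mean adherence between the three supports but specifies no measure of spread or precision; small numbers are a reason to show an interval, and the text does not exclude one

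*Combined protocol and SAP*

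**What the plan says.** Section 10b (Tablet counts) plans a descriptive analysis. Tablets are counted at each focus group discussion (FGD), and the eligible period runs from the first antenatal visit, when the tablets were received, to the date of that discussion. It then says: "Adherence will be measured after the completion of each intervention, and differences in the mean will be measured". On inference it adds: "However, due to a very low sample size, no statistical test will be applied". Section 10c repeats that sentence for the acceptability percentages. Neither section names an SD, range, standard error or interval.

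The comparison has a stated purpose. Section 3 says that with this design "researchers can see which approach works best", and couples this with use of the women's feedback.

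Section 7a fixes the structure: "Each enrolled woman receives all interventions in a specific sequence". The same women are therefore counted after A, after B and after C. Section 5 says "the sample size of 48-60 women (around 12-15 women per province) is purposive" and justifies the number by focus group size and saturation, not by precision.

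**The concern.** A difference in means that is meant to show which of three supports works best needs some statement of how well it is estimated. The plan answers small numbers by declining to test, which is reasonable, but puts nothing in the test's place. Small numbers make precision more important to show. An interval is an estimate and fits the descriptive aim.

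Without one, a reader given three means will tend to rank them. If adherence differs by two or three points, the ranking may reflect only which women came and how their counts happened to fall. The same women are counted each time, so the data for a within-woman interval are already being collected.

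**Working it through.** **Plan's own figure.** Four provinces with 12-15 women each: 4 × 12 = 48 and 4 × 15 = 60, as stated. Section 5 allows for absence: "if 20% of the participants are expected not to show, there would still be enough participants to conduct an FGD". With 20% absent, 12 × 0.8 = 9.6 and 15 × 0.8 = 12 attend per province, which meets the target of 8-10 in Section 6. There is no power or precision calculation to reproduce.

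**Women with counts.** Counts are made at the focus groups (Section 7f), so attendance sets n.
- One round: 48 × 0.8 = 38.4 to 60 × 0.8 = 48, so about 38-48.
- Two given rounds, if absences are independent (an assumption): 48 × 0.8² = 30.7, so about 31 at the lower enrolment.
- Full attendance: up to 60.

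**Half-width of the paired 95% interval** = t(0.975, n−1) × SD / √n, where SD is that of the within-woman difference in percent of tablets taken. The documents give no SD; 15-25 points is assumed.

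| n | t/√n | SD 15 | SD 20 | SD 25 |
|---|---|---|---|---|
| 31 | 0.367 | 5.5 | 7.3 | 9.2 |
| 38 | 0.329 | 4.9 | 6.6 | 8.2 |
| 48 | 0.290 | 4.4 | 5.8 | 7.3 |
| 60 | 0.258 | 3.9 | 5.2 | 6.5 |

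The range is 3.9-9.2 points. An observed difference of two or three points lies within the half-width in every cell.

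**What the interval would be placed on.** As defined in 10b, adherence is cumulative. With equal periods and period-specific adherence a, b, c, the three values are a, (a+b)/2 and (a+b+c)/3. Hence:
- second minus first = (b − a)/2, half the period difference;
- third minus second = [c − (a+b)/2]/3.

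For example, period values of 70, 80 and 90% would be reported as 70, 75 and 80%. Steps of 10 points appear as steps of 5. An interval on the cumulative values would describe an attenuated difference, so period-specific values must come first.

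This affects n. Adherence under C needs the second and third counts, so C−A and C−B need all three. With independent absences, 48 × 0.8³ = 24.6, about 25 women at worst. The factor is then 0.413 and the half-width 6.2-10.3 points for SD 15-25. B−A needs only the first two counts.

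**By province.** At SD 20, n = 8, 10, 12 and 15 give factors of 0.836, 0.715, 0.635 and 0.554, hence half-widths of 16.7, 14.3, 12.7 and 11.1 points. Intervals at that level would say little.

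**Acceptability.** Under 10c this is one unpaired percentage per statement. Illustrative Wilson 95% intervals near 80% agreement are 63.7-88.9% (30/38), 65.7-88.3% (38/48) and 68.2-88.2% (48/60).

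**The case against.** The strongest reply is that this is a small, formative, mainly qualitative study. Its aims in Section 2 are preferences, barriers, co-design and packaging. The sample is purposive, so the population an interval refers to is unclear, and declining to test is a fair choice. That limits the weight of the point. It does not remove it, because the plan itself computes differences and says the design shows what works best.

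Four stronger readings are tempting, and the documents do not support them.

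- *That the plan forbids any measure of uncertainty.* It excludes tests. The absence of an interval is silence, and a descriptive analysis could include an SD or an interval.
- *That pairing makes the three supports comparable, so an interval would validate a ranking.* Section 7a gives one fixed sequence with no allocation, and Section 7c has family reminders continuing until the 180 tablets are finished, so A runs into B and C. Order, time and carry-over stay mixed with the intervention whatever interval is shown. An interval that excludes zero could even lend weight to a ranking that the design cannot support.
- *That the acceptability results share the ranking problem.* Section 7g describes a survey of taste, smell, size, color and ease of swallowing. It does not compare the supports, and under 10c it is asked at the first focus group only.
- *That tablet counts alone will decide what is scaled up.* No section says so.

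**Conclusion.** The point holds as a modest, inexpensive improvement to 10b. The plan compares mean adherence between supports with a stated interest in which works best, and specifies neither spread nor precision. With 31-60 women contributing two counts and an assumed SD of 15-25 points, the 95% half-width is about 4-9 points. It reaches about 10 for the comparisons with C if only 25 women have all three counts. Differences of a few points could therefore not be told apart from zero.

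The result rests on the assumed SD and, for n = 31 and n = 25, on independent absences at the lower enrolment. The calculation treats women as independent although they come from four health centers. The interval is useful only on period-specific adherence, and even there it limits what may be read into small differences. It does not establish that one support is better.

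**What to change.** In 10b, keep the decision not to test and add the following.

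1. Derive adherence for each intervention period by subtracting consecutive tablet counts, allowing for any tablets supplied in between, and divide by the days between counts. Say how the first period is handled: it starts on receipt of the tablets, and no count is planned at the start of Intervention A.
2. Report mean within-woman differences (B−A, C−A, C−B) in percent of tablets taken, with SD, 95% confidence interval and the number of women with the counts needed, overall only.
3. By province, give n, mean and SD only.
4. State before the results that the intervals are descriptive and cover sampling error only. They do not address the fixed A-B-C order, carry-over of family support, the purposive sample or the four sites.

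Optionally, in 10c, give n and a Wilson or exact 95% interval for each agreement percentage. Also reconcile the survey's timing: 10c places it at the first focus group, while Section 3 describes acceptability data in the context of the discussion after each intervention.

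The cost is a few sentences and minutes of analysis, with no new data. The downside is that an interval may be read as evidence of cause, which the statement in item 4 is there to prevent.
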